The proposed study builds on the Medical Research Council guidelines for the development and evaluation of complex interventions. We have conducted research to explore the theoretical validity of the intervention and synthesized this theoretical approach with the current evidence base and the views of potential participants in order to model an appropriate intervention approach. We have tested the feasibility of implementing the intervention in the target population and refined the intervention and its delivery as a result of that feasibility study. We have conducted an appropriately designed pilot study to explore potential effectiveness on the key parameters and found evidence of potential effect in reducing substance use and risk-taking behaviour and high levels of satisfaction and engagement. As the proposal involves a specific population, those engaged with the criminal justice system rather than adolescents per se, we have conducted a second feasibility study in this population to assess feasibility and acceptability and found high levels of engagement and acceptability in this population. The next step is to conduct a rigorous evaluation to address key outcomes in a way that provides valid scientific evidence and is useful to those engaged with this population and commissioners of services. To this end we have proposed a full, multi-centre randomized controlled trial, with an embedded qualitative component, of the intervention versus treatment as usual to explore the effectiveness of the intervention; in reducing substance use, improving mental-wellbeing, reducing criminal activity that is economically viable to implement and acceptable to the target population.

6.4 Intervention process: RISKIT-CJS is delivered in 4 steps consisting of two oneto-one sessions lasting approximately one hour and two half-day group sessions over two consecutive weeks. Groups are delivered in premises managed by KCA/Addaction by trained and experienced specialists in the delivery of therapeutic interventions to young people who are provided with ongoing supervision and support. The mean group size is 6 participants. Details of the intervention are contained in the RISKIT manual, (http://mentoradepis.org/wp-content/uploads/2013/05/RisKit-Operational-Manual.pdf).

The intervention involves four distinct steps.

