7.2 Secondary objectives

- To evaluate the cost-effectiveness of the intervention compared with treatment as usual.
- To explore participants and criminal justice staff experience of the intervention and the acceptability of the methods employed.
- To assess the fidelity with which the intervention is conducted and explore the role of fidelity, therapeutic alliance and baseline psychological factors on the outcomes observed.
- If the intervention is shown to be effective within the parameters set to develop a protocol for dissemination and integration of the intervention in current practice.

8. Study design: Mixed method, prospective, pragmatic randomized controlled trial with individual allocation, combining both quantitative and qualitative evidence. The study will be conducted across three geographical areas; South East England, South London, North East England, covering a diverse socio-economic and ethnic population.

9. Outcome trial assessments

9.1 Baseline assessments: Research staff will meet with participants at a prearranged appointment. Eligibility will be assessed and those eligible provided with a written and verbal description of the study and invited to consider participating. If a participant is willing to participate consent will be taken for those aged 16 or more or those considered by the YOT staff as being 'Gillick competent'. For those not considered 'Gillick competent' caregivers will be contacted and asked to provide informed consent. Once consent is received baseline assessment will be undertaken and data recorded on a secure IPad using a specifically designed study application. The baseline assessment consists of a combination of researcher-led and self-completed outcomes with the option of allowing self-completed outcomes to be completed by interview for those who have difficulties in reading English. Baseline assessment is estimated to take 30 minutes and immediately after assessment allocation will occur and the participant informed of their allocation. In addition to providing the allocation the randomization system will allocate the participant to an intervention group with a start date and location. All participants will be thanked for their time and provided with a £10 voucher as compensation for their time and to reduce attrition in the follow-up sample [30]. Confirmation of group and time will be made by phone, email or post after the allocation.

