11.1 Training: Existing intervention staff will be augmented with new staff in locations where RISKIT is not currently available, North East England. Existing experienced youth workers, employed by KCA/Addaction, will be trained using an existing training package by training staff from the South East area. The training is provided over two days and covers; theoretical underpinnings, delivering programme elements, managing groups, individual motivational interviews, managing risks and safeguarding. A full intervention manual, covering training and practice, is available for interventionists; senior practitioners will observe practice and deem practitioners as competent prior to embarking on the RISKIT programme. Supervision is provided by senior staff with experience of delivering the intervention throughout the study period. In addition, all interventionists will attend a half-day training session on trial procedures and outcome assessment prior to the start of recruitment.

11.2 Control Intervention: Guidelines suggest that interventions should be provided for adolescents within CJS settings who score 2 or more on ASSET, ASSET Plus or equivalent for substance use. But the reality is that those with no immediate clinical need for treatment, in the form of detoxification or substitution are unlikely to receive an intervention, rather existing services are signposted and rates of engagement are low [6]. When intervention is provided it often takes the form of short duration brief behavioural change interventions with limited evidence of effectiveness in substance using population [39].

12. Randomisation: Allocation conducted at the level of the participant and conducted independent of the research team using random permuted blocks of variable length. Randomisation strings are generated by Codeface Ltd and encrypted and stored within the baseline data collection tool. To allow for the most efficient use of resources differential allocation will be employed with twice as many participants allocated to the control group compared with the intervention group. Power calculations have been adjusted to reflect the allocation ratio. Allocation will include stratification by gender, Youth Offending Team (YOT) and age (13-15 years versus 16-17 years).

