15.1 **Sample size calculation:** For the effectiveness analysis is designed to identify a clinically important difference of 0.3 for the primary outcome measure, percent days abstinent from all substances at 12 months post-randomisation in addition to a clinically important difference of the secondary outcome measure of mental health wellbeing, measured using the WEMWBS. In order to detect an effect size difference of 0.3, with alpha of 0.05 at 80% power using a two-sided test requires 175 analysed at 12 months in each of the two groups, a total of 350. As the intervention is intensive and potentially costly to implement we have increased the efficiency of the study by allocating participants in a 2:1 ratio, with twice as many allocated to the control condition. As differential allocation leads to a loss of power we have maintained the integrity of the sample size calculation by increasing the numbers required; 264 in the control group and 132 in the intervention group, a total of 396. Our previous studies with adolescents and those involved in the criminal justice system (SIPS-CJS, RISKIT) suggests that loss at 12 months is likely to be somewhere in the region of 15 to 30% and we have adjusted the required sample to account for a 30% loss at 12 months. This inflates the required number to 567; 378 in the control group and 189 in the intervention group. Between 2013 and 2014 the mean number of potentially eligible participants across the participating regions was 5200, with a prevalence of ASSET score 2 or more ranging between 32 and 42%, of these we estimate 80% will meet all other eligibility criteria. Based on these estimates we require a consent rate of the order of 40% in order to achieve our estimated sample size estimation over the recruitment period. Our experience in the feasibility study suggests that 60% of those eligible are likely to consent.

The qualitative component of the study will be purposive and include group discussion with participants in the intervention group and individual interviews with staff in participating YOT's. Participants will be chosen purposively in order to provide diversity in terms of site, and age and ensure appropriate participation by gender, social class and ethnicity. The sample size considerations of the qualitative component are driven by the need to achieve data saturation, the point at which no new themes are emerging from the data, and this

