needs to be judged in practice. Our previous experience of similar studies estimate the participants needed to be of the order of 12 groups and the number of staff in YOT to be of the order of 24.

15.2 Effectiveness analysis: Effectiveness analysis will be conducted by treatment allocation using a two-sided 5% significance level. Analysis and results will be presented in accordance with CONSORT guidelines. The primary outcome is percent days abstinent from substance use in the 28-days prior to the 12-month follow-up. After checking for distributional assumptions and making any appropriate transformations this will be analysed using an analysis of covariance adjusting for baseline values and stratification values used in the allocation process; age, gender and centre. Results will be presented as mean differences between the groups and the associated 95% confidence intervals. Missing data will be assessed using multiple imputation approaches to model missing data scenarios and sensitivity analysis will be conducted to explore the relative impact of missing data on the observed outcome. Secondary outcomes will be analysed in a similar manner.

Analysis will also be undertaken to model the relationship between pre-randomisation factors and observed outcome at 12-months; demographics, self-efficacy, readiness to change. This analysis will employ a linear regression model including interaction terms for allocated group. To further enhance our understanding, we will additionally incorporate an analysis of process by enhancing the prognostic analysis by including measures of adherence, fidelity, derived from the BECCI ratings, and therapeutic alliance.

Exploratory sub-group analysis will be undertaken to model the relationship between gender, ethnicity and social class measured using index of material deprivation from postcode on observed outcome.

15.3 Cost-effectiveness analysis: The effectiveness analysis will be complemented by an economic evaluation that will evaluate the economic implications of the intervention versus treatment as usual. Substance use generates high costs for the individual, health service and society in general and the economic analysis will be conducted first using a narrow health and social care perspective, to concord with NICE guidelines for the conduct of health economic evaluations and second using a wider public sector perspective incorporating costs associated with employment, training, education and criminal justice.

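### Only the intervention arm is treated in groups, but the sample size and primary ANCOVA assume independent participants, so any within-group correlation makes the primary standard error too small

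*Protocol*

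**What the plan says.** Section 12 of the protocol randomises individuals, two to control for each one to intervention. Section 6.4 describes two one-to-one sessions and two group sessions of half a day each for the intervention arm, and states: "The mean group size is 6 participants". Section 9.1 adds that "the randomization system will allocate the participant to an intervention group with a start date and location". Section 11.2 describes control as usual care, largely signposting to existing services, with no trial group.

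Section 15.1 gives the basis of the sample size: "In order to detect an effect size difference of 0.3", "with alpha of 0.05 at 80% power using a two-sided test", the trial "requires 175 analysed at 12 months in each of the two groups, a total of 350". It then moves to 264 control and 132 intervention for the 2:1 ratio, and to 378 and 189 for 30% loss. It states no ICC or design effect.

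In section 15.2 the primary outcome, percent days abstinent, is "analysed using an analysis of covariance adjusting for baseline values and stratification values used in the allocation process; age, gender and centre". Secondary outcomes are to be handled in a similar way.

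**The concern.** Individual randomisation with group delivery in one arm only is a partially nested design. Members of an intervention group share sessions, facilitators and peers; controls share nothing of the kind. Their 12-month outcomes may therefore correlate within groups. The protocol gives some reason to expect this: section 6.3 treats peer influence as something that group delivery has to manage.

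If there is such correlation, 132 intervention outcomes carry less information than 132 independent ones. An ANCOVA without a group term then understates the standard error of the treatment effect. The confidence interval for the primary outcome is too narrow and a nominal 5% test rejects too often. The power in 15.1 is also overstated on its own terms. The clustered arm is the smaller one, which under independence already supplies two thirds of the variance of the difference, so the 2:1 ratio makes the effect worse.

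**Working it through.** **Inputs from the protocol.** Standardised effect 0.3 (SD taken as 1), two-sided alpha 0.05, power 80%, 264 control and 132 intervention analysed, 30% loss (section 15.1); mean group size 6 (section 6.4).

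**Assumptions.** ICC from 0.01 to 0.10, because the protocol gives none. Analysed group size m between 6 × 0.7 = 4.2 (loss spread evenly over groups) and 6. Normal approximation, no credit for the baseline covariate.

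**Step 1: reproduce the plan under independence.** Let K = (1.960 + 0.842)² / 0.3² = 87.2.
- 1:1 allocation: 2K = 174.4, so 175 per arm, as stated.
- 2:1 allocation: intervention n = 1.5K = 130.8, so 131, with 262 controls. The protocol's 132 and 264 are slightly above this.
- SE at 264/132 = √(1/264 + 1/132) = 0.1066; power = Φ(0.3/0.1066 − 1.960) = 80.4%.
- Loss: 264/0.7 rounds up to 378 and 132/0.7 to 189, total 567, as stated.

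The figures follow from independence alone, so no clustering allowance is hidden in them.

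**Step 2: allow for groups in the intervention arm only.** Number of groups: 189/6 = 31.5, about 32. Design effect DE = 1 + (m − 1) × ICC. Then:
- true SE = √(1/264 + DE/132)
- power = Φ(0.3/true SE − 1.960)
- true error of the unadjusted test = 2 × [1 − Φ(1.960 × 0.1066/true SE)]

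Example, m = 6 and ICC 0.05: DE = 1.25, true SE = 0.1151, power 74.1%, true error 7.0%.

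| ICC | DE (m = 4.2 to 6) | True SE / naive SE | Power | True type I error |
|---|---|---|---|---|
| 0.01 | 1.03-1.05 | 1.01-1.02 | 79-80% | 5.2-5.4% |
| 0.02 | 1.06-1.10 | 1.02-1.03 | 78-79% | 5.5-5.8% |
| 0.05 | 1.16-1.25 | 1.05-1.08 | 74-76% | 6.2-7.0% |
| 0.10 | 1.32-1.50 | 1.10-1.15 | 68-72% | 7.5-9.0% |

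Over ICC 0.02 to 0.10 the true SE is 2-15% larger than the naive one; equivalently, the naive SE is about 2-13% too small (1 − 1/1.155 = 13.4% at the extreme).

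**Step 3: how much slack is there?** For 80% power the SE may be at most 0.3/2.802 = 0.1071. Solving for DE and taking m = 6 gives ICC ≈ 0.003.

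**Step 4: small-sample degrees of freedom.** With 22 groups analysed (132/6) to about 31 (132/4.2), Satterthwaite degrees of freedom lower power to 72-75% at ICC 0.05 and 66-71% at ICC 0.10.

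**Step 5: credit for baseline.** With baseline-outcome correlation r, multiply the SE by √(1 − r²). At an assumed r = 0.4, power (normal approximation) is 81-83% at ICC 0.05 and 76-80% at ICC 0.10. At r = 0.5 it is 80-84% at ICC 0.10. The factor applies to the naive and true SE alike, so their ratio, and the excess type I error, do not change.

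**The case against.** **The ICC may be very small.** The group element is two half-day sessions alongside individual work, and the outcome covers 28 days before a 12-month follow-up. No ICC for this programme is shown, and at 0.01 the loss of power is about one point. This stands: the size may be negligible, and the point has to be conditional.

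**Power may still reach 80%.** A reader might infer that the trial fails to deliver its stated power. The documents do not support that. The planned ANCOVA adjusts for baseline, section 15.1 takes no credit for it, and a moderate correlation would make up the loss at ICC 0.05. What remains is the error rate, which baseline adjustment does not correct.

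**The statistical analysis plan could add a group term.** It could, and it is not shown. But the protocol itself names the primary model and fixes the sample size, and both leave out a design feature that it describes elsewhere.

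**Centre and YOT.** A reader might also infer that the model adjusts for a coarser unit than the Youth Offending Team used in stratification, and so loses precision. Section 15.2 defines its covariates as the stratification values used in allocation, so centre can be read as the YOT. Only a mismatch of terms remains. On that reading the model might also absorb some between-group variation, but the protocol does not say how groups map to YOTs, so it cannot be relied on to do so.

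**Conclusion.** The point holds in conditional form. The design is partially nested, the sample size reproduces only under independence, and the named primary model has no term for treatment group. The direction follows for any positive ICC: standard error too small, type I error above 5%. The size is not known. It runs from negligible at ICC 0.01 to moderate at ICC 0.10 (type I error 7.5-9.0%, and 68-72% power before any baseline credit). These figures rest on the assumed ICCs, 4.2 to 6 analysed per group, equal total variance in the two arms and the normal approximation. The effect on the validity of the primary test is the main matter; the effect on power is secondary and may be offset.

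**What to change.** 1. **Section 15.2.** Make the primary model, and the matching secondary models, a partially nested mixed model: a random intercept for allocated treatment group in the intervention arm only (each control its own unit), arm-specific residual variance and small-sample degrees of freedom. Use the group allocated by the randomisation system, not the group attended, so that the analysis stays by allocation.
2. **Section 15.1.** Keep the enrolment target. Say that 80% power holds only under independence. Give the power over a stated ICC range by a method that matches the model, including its degrees of freedom, and state explicitly any credit taken for baseline adjustment.
3. **Wording only.** Write YOT in 15.2 in place of centre, to match section 12.

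The cost is text in two sections, a slightly less favourable power statement and possibly a slightly wider confidence interval. No further participants or data are needed.

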Summary of Participant Population: Adolescents aged between 13 and 17 years currently involved in the criminal justice system (CJS) and engaged with a participating YOT who score 2 or more on the ASSET, ASSET Plus, or equivalent assessment tool for substance use. Identification of participants will be conducted in collaboration with YOT staff and baseline assessment conducted by trained staff from KCA/Addaction. Interventions will be conducted in suitable locations; youth or substance use facilities by KCA/Addaction staff and follow-up conducted by research staff in similar facilities.

Planned Sample Size: We aim to recruit 567 participants over a 12-month period with the aim of assessing at least 396 of these at the 12-month assessment. We estimate a loss to follow-up at the primary end point, 12 months post-randomisation, of 30%. Our sample is designed to identify a clinically important effect size difference of 0.3 in the primary outcome measure, percent days abstinent from all substances, with an alpha of 0.05 and power at 80% using atwo sided test.

Planned Number of Sites: The study will be conducted across three geographical areas; South East England, South London, North East England

Study Intervention: Participants in the intervention group will receive the RISKIT-CJS intervention in addition to any treatment as usual. Groups are delivered in premises managed by KCA/Addaction by trained and experienced specialists in the delivery of therapeutic interventions to young people who are provided with ongoing supervision and support. The mean group size is 6 participants.

Follow Up Duration: Follow up will be conducted at 6 months and 12-months post intervention; completion of a questionnaire.

Planned Trial Period: 01 September 2016 – 30 August 2019

6. Study Protocol

6.1 Background: Adolescence is a critical developmental stage when young people make behavioural and lifestyle choices that have the potential to impact on their health and wellbeing into adulthood. While risk-taking is important for healthy psychological development, for many, inappropriate risk-taking is significantly associated with health and social harm during adolescence and these harms persist well into adulthood [1].

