The participatory consultation was adapted from participatory action research [21, 22] and was carried out with a number of groups of young people. The aim of the exercise was to establish, with young people what they perceived as risk-taking behaviour, why they took risks, the consequences of taking risks and how they perceived the problems could be addressed. The main themes in terms of risk-taking behaviour centred around; criminal activity, substance use and sexual activity and these activities considered as being linked. The participants considered prevention programmes, that focus on the negative outcomes of risk, failed to appreciate that risk-taking can be positive and lead to positive outcomes an issue highlighted by other research exploring the processes associated with risk-taking [18, 23]. The young people highlighted the need for some education regarding risks and consequences, but particularly highlighted the preference for interventions that provided skills and strategies to manage risk and the opportunity to discuss these skills with peers and to learn how to implement them. Interestingly parental influences were not considered critical to any intervention and many considered parental involvement would be inappropriate and unacceptable. The primary focus for the young people was not on eradication of risktaking but rather a focus on how risk could be reduced and the negative consequences minimised.

We consulted a number of existing reviews and research studies [24-29] and found that while there is a growing body of research in the field there is a paucity of rigorously evaluated interventions with the majority of research arising from the US with limited applicability to the UK. Of importance was what has been proven not to work, this includes focusing on negative aspects of risk and risk abstinence. Promising intervention approaches included motivational interviewing and cognitive and socio-emotional life skills training. In addition there was emerging recognition of the importance of providing interventions in a structured manner and with the young people's preference for peer group interventions the importance of managing the potentially negative effects of labelling and peer influence.

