Step 1 of the intervention entails a single face-to-face session using motivational interviewing approaches to discuss current substance use, risk-taking behaviour, and support for behaviour change and enhance motivation to engage with the intervention.

Step 2 involves a group session over half a day at a location convenient for the participant. This session addresses a number of key issues involving both psychoeducation and skill development including; understanding substance use and associated harms, understanding triggers of substance use behaviour, strategies for managing and minimizing risk, strategies for diversion and distraction and sexual health.

Step 3 is conducted a week later at the same location as step 2 and involves a similar group approach. At this session, issues covered include communication strategies and assertiveness training, managing anger and mindfulness and planning for the future.

Step 4 is a single one-to-one session using a motivational interviewing approach that addresses outstanding barriers to change, managing expectancy and enhancing self-efficacy to change. At this stage, interventionists work with participants to identify local service contacts that may be useful.

Each step of the intervention is delivered on separate days; over a four-week period to allow for any behaviour change may occur to be the focus of step 4.

7. Research aim and objectives

7.1 Primary objective: To conduct a prospective pragmatic randomised controlled trial to evaluate the effectiveness of the RISKIT-CJS intervention compared with treatment as usual for substance using adolescents involved in the criminal justice system.

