15.5 Qualitative analysis: The aim of the qualitative component of the proposal is to explore participants' and practitioners' experience of the RISKIT-CJS intervention in order to generate information pertaining to the feasibility, acceptability, contextual influences and mechanisms of action. The qualitative design consists of two elements; the first is participatory group work with participants who have experienced the RISKIT-CJS programme and the second telephone interviews with practitioners who work with these participants. Thematic coding of qualitative data will be carried out using specific software (QSR NVIVO) that allows for the coding of both verbal, transcripts and field notes, and visual data. The coding allows for the identification of recurrent and important themes and the generation of a framework of themes relating to the key research questions and objectives. A detailed description of themes will be presented. Emergent themes that may be explored from the quantitative data analysis will be incorporated into the analysis plan as secondary exploratory analyses.

16. Compliance and withdrawal

16.1 Assessment of compliance: Visits to the individual YOT's in the geographical sites will be conducted by research staff to ensure compliance with protocols.

16.2 Withdrawal of participants: Participants have the right to withdraw from the trial at any stage. Reasons for withdrawal will be recorded. Participants can withdraw from the study completely, whereby all trial data previously collected will be deleted. They may withdraw from the study partially whereby no further data collection will be undertaken. They may withdraw from any allocated intervention but agree to adhere to any future follow-ups.

17. Data monitoring, quality control and quality assurance

This is a low risk trial. The University of Kent and the /NIHR PHR Programme have therefore agreed that the TSC will also monitor trial data in place of a separate Data Monitoring and Ethics Committee (DMEC). To this end, independent members may access unblended study data and meet in closed session. The main areas of focus will include informed/consent, recruitment, data quality and completeness of documentation.

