Following the initial meeting, the TSC will meet annually. Its role is to oversee the trial to ensure it is conducted to high standards in accordance with the protocol, the principles of Good Clinical Practice (GCP) applied to non-drug trials, and relevant regulations and guidelines. This committee will also take responsibility for the ethical compliance of the trial. The purpose of this committee will be to monitor efficacy and safety endpoints, although only independent members may have access to unblinded study data. Written Terms of Reference will be agreed by the TSC. All monitoring findings will be reported and followed up with the appropriate persons in a timely manner. The study may be subject to inspection and audit by the University of Kent under their remit as sponsor, and other regulatory bodies to

ensure adherence to GCP. The investigators' institutions will permit ethical review, trialrelated monitoring and audit, and regulatory inspection(s), and provide direct access to source data and documents.

All monitoring findings will be reported and followed up with the appropriate persons in a timely manner. In case of adverse events deemed a serious, the chair of the TSC will form an extraordinary DMEC, where members who will follow good practice guidelines in assessing the relationship between events and the process of the trial and take any appropriate action. The study may be subject to inspection and audit by the University of Kent under their remit as sponsor, and other regulatory bodies to ensure adherence to GCP. The investigators/ institutions will permit trial-related monitoring, audits, ethical committee review and regulatory inspection(s), providing direct access to source data/documents.

18. Adverse event monitoring and reporting: Due to the nature of the study it is not expected that participants will experience any adverse events/serious adverse events during the study. In the event that the participant reports an event related to the study during a study visit this will be reported on an adverse event form and fully investigated by the CI. Each site principal investigators will assess the adverse even following the CONSORT guidelines[41] (see annexe). All adverse events will be reported to the TSC chair.

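### The committee given the safety role meets once a year, so about one scheduled meeting falls within the 12-month recruitment period, and no review of accumulating data by arm is scheduled

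*Protocol*

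**What the plan says.** **Who monitors.** Protocol section 17 calls the trial low risk and records that the university and the funder agreed the TSC would monitor trial data instead of a separate DMEC. It continues: "The purpose of this committee will be to monitor efficacy and safety endpoints, although only independent members may have access to unblinded study data". Section 20 nevertheless lists a separate DMEC alongside the TSC and gives it no meeting schedule.

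**On what.** Section 17 also states: "The main areas of focus will include informed/consent, recruitment, data quality and completeness of documentation". Safety is not on that list. Independent members are permitted to see unblinded data in closed session, but no such session is scheduled.

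**When.** "Following the initial meeting, the TSC will meet annually". The initial meeting is not dated. Written Terms of Reference are still to be agreed.

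**Trial calendar.** Section 5: "We aim to recruit 567 participants over a 12-month period". Section 14 places recruitment in months 7 to 18, after set-up in months 1 to 6. Section 6.4: "Each step of the intervention is delivered on separate days; over a four-week period".

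**Between meetings.** Section 18 sends all adverse events to the TSC chair. Section 9.6 sends events rated as possibly related to the TSC. Under section 17 a serious event leads the chair to form an extraordinary DMEC. The serious-event list in section 9.6 is broad. It covers emergent substance use needing specialist referral, worrying changes in offending, safeguarding disclosures and any potentially iatrogenic effect.

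**The concern.** The intervention brings together substance-using 13 to 17-year-olds in groups. In describing the evidence behind it, section 6.3 notes "the importance of managing the potentially negative effects of labelling and peer influence". Harm of that kind would show mainly as somewhat more substance use or offending in one arm. Both are common in this population (section 6.2 puts recidivism at 36%), so a single relapse or arrest can rarely be attributed to the groups. An excess in one arm can be seen only when events are added up by arm.

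The body charged with safety therefore needs to look at accumulated data while some participants have still to be allocated. An annual calendar set against a 12-month recruitment period and a four-week course gives it about one scheduled opportunity. That opportunity lands wherever the undated initial meeting happens to put it, and nothing requires the data to be examined by arm.

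**Working it through.** **1. The plan's arm sizes.** Inputs from section 15.1: standardised effect 0.3, two-sided 5%, power 80%, 2:1 allocation, 30% loss.
- At 1:1: n per group = 2 × (1.96 + 0.842)² / 0.3² = 174.4, so 175, as stated.
- At 2:1 the same formula gives 262 + 131 = 393. The plan has 264 + 132 = 396 (power 80.4%), which is slightly generous.
- After loss: 264 / 0.7 = 377.1, so 378; 132 / 0.7 = 188.6, so 189; total 567, as stated.

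The intervention arm is taken as 189 below.

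**2. Scheduled meetings within recruitment.** Meetings 12 months apart against a 12-month window give about one meeting in the window, wherever the cycle starts. This step needs no assumed dates.

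**3. Share allocated at the first annual meeting.** Two assumptions are not in the Protocol: uniform accrual over months 7 to 18, and an initial meeting in set-up at t₀ elapsed months. The first annual meeting is then at m = t₀ + 12.
- Allocated = (m − 6) / 12.
- Past the four-week programme (taken as one month, starting at allocation) = (m − 7) / 12.
- 6-month data due = (m − 12) / 12.

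| t₀ | m | Allocated | of 189 | Past programme | 6-month data due, of 189 |
|---|---|---|---|---|---|
| 0 | 12 | 50% | 94 | 42% | 0 |
| 1 | 13 | 58% | 110 | 50% | 16 |
| 2 | 14 | 67% | 126 | 58% | 32 |
| 3 | 15 | 75% | 142 | 67% | 47 |
| 4 | 16 | 83% | 158 | 75% | 63 |
| 5 | 17 | 92% | 173 | 83% | 79 |
| 6 | 18 | 100% | 189 | 92% | 94 |

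The following meeting is at months 24 to 30. Allocation ends at month 18 and the last four-week course about a month later, so treatment is over by then.

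**4. Sensitivity to the initial meeting.** If it precedes month 1, the share at the first annual meeting is below 50%. If it comes after set-up, the first annual meeting falls after recruitment closes, and the only scheduled meeting within recruitment is the initial one.

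**5. What a recruitment-timed review could see.**
- One quarter randomised is the end of month 9 and one half is the end of month 12. 6-month data due at both: none.
- Three quarters is the end of month 15. 6-month data due: 0.25 × 189 ≈ 47 intervention and 0.25 × 378 ≈ 94 control, before attrition.
- Power there for 0.3 SD: standard error = √(1/47 + 1/94) = 0.179; 0.3 / 0.179 = 1.68; Φ(1.68 − 1.96) ≈ 39%.

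**6. Comparability of event counts.** Section 9.6 defines an adverse event as arising in someone who has been given a study intervention, and one serious-event criterion depends on what interventionists see or are told. On that wording, equal capture in the control arm is not assured.

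**The case against.** The strongest reply is that review here is event-driven and need not wait for the calendar. The serious-event list in section 9.6 reaches the substance-use and offending harms at issue, any event deemed serious convenes an extraordinary DMEC, and that group may consider the process of the trial and act. All events reach the TSC chair, and a management group meets monthly (section 20). A reader might infer that nothing protects participants between annual meetings. The documents do not support that, and these routes are real safeguards. However, they start from reported events and ask how those events relate to the trial. None calls for a tabulation by arm, and the management group consists of investigators, staff, collaborators and a lay member, whereas section 17 limits unblinded data to independent TSC members.

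A second reply is that follow-up lag, rather than the meeting calendar, limits what can be detected. This stands in large part: steps 5 and 6 show no 6-month outcomes by mid-recruitment, weak power at three quarters and event counts that may not be comparable. It argues for a modest and descriptive review, with equal capture of events. It does not argue for leaving the review to chance.

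A third reply is that sponsor and funder accepted the arrangement for a low-risk trial and that details belong in the Terms of Reference. Low risk may justify doing without a separate committee. It does not explain assigning a safety role on a calendar that serves it poorly, although the Terms of Reference are a sensible place for part of the remedy.

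Two further inferences go too far. One is that the Protocol schedules a by-arm review and merely holds it late; it only permits access to unblinded data. The other is that it has no separate monitoring committee at all; section 17 says so, but section 20 names one.

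**Conclusion.** The point holds as a low-cost improvement that should be made. On the text alone, section 17 gives the TSC the safety role, omits safety from its focus and schedules it annually. About one scheduled meeting therefore falls within recruitment, no passage schedules a look at accumulated data by arm, and section 20 conflicts with section 17 on which body is responsible.

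The 50% to 100% range (94 to 189 of 189 allocated by the first annual meeting) is not a Protocol figure. It rests on uniform accrual and an initial meeting in months 1 to 6, and it moves as step 4 describes. The finding does not show that a harm would be missed, or that earlier meetings would reliably detect one. It shows that the planned schedule gives the independent members little assured opportunity to look while allocation can still be influenced.

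**What to change.** 1. Reconcile the statements in section 17 with section 20 so that one named body holds the safety-monitoring role, and add safety to the areas of focus in section 17.
2. Time closed sessions of the existing independent members to recruitment, for example at about one half and about three quarters randomised. The first would see serious events by arm, since no 6-month data exist by then. The second would add the 6-month outcomes due, read descriptively given the limited power.
3. In section 9.6, define and record adverse events identically in both arms, so that the by-arm table can be interpreted.
4. Leave any threshold for action to the committee, to be set out in its Terms of Reference.

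The cost is one or two short extra sessions, one by-arm table, and wording changes to the Protocol and Terms of Reference. Event recording in controls would need to match that in the intervention arm. No new committee is needed. The limitation is that power to detect an average harm during recruitment remains low.
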